#### **2.4.8 Analyses of pharmacokinetics variables**

Concentrations of total alirocumab in serum ( $C_{trough}$ ,  $C_{max}$  and  $C_{Follow-up}$ ), free and total PCSK9 concentrations will be summarized on the PK population by treatment group and visit using descriptive statistics.  $C_{trough,av}$  will be summarized on the PK population by treatment group using descriptive statistics. These summaries will be also provided by dose in the alirocumab group to explore the impact of up-titration on concentrations ( $C_{trough}$ ,  $C_{max}$  and  $C_{Follow-up}$ ). Descriptive statistics could be provided by specific sub-groups (eg, gender, BMI, age), as needed.

Time profiles for  $C_{trough}$  concentration, total and free PCSK9 will be also provided by treatment group using graphs (mean  $\pm$  SE or Median, as appropriate).

Additional plots will be prepared, as deemed necessary (eg, to explore the relationship with some safety or efficacy endpoints of interest).

Concentrations of total alirocumab in serum and PCSK9 levels might be used for population PK modeling if considered necessary and the results of population PK modeling will be reported separately from the study report.

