The current and most relevant evidence around the effects of achieved low LDL-C levels comes from examinations of large statin trials (30, 31, 32) and patients with PCSK9 loss-of-function mutations (33). The patients achieving the lower levels of LDL-C had the lower CV event rates. To date, there is no evidence that very low LDL-C levels result in significant adverse health effects based on these sources of information, though this conclusion is based on a relatively low number of patients with very low LDL-C who have been studied.

Based on the results of the two dose finding studies, the Q2W dosing regimen best maintained constant LDL-C lowering throughout the interdosing interval, with the maximum efficacy at 12 weeks provided by the 150 mg Q2W dosing. However, for many patients, the magnitude of effect observed with the 150 mg Q2W dose may not be needed to achieve the target LDL-C goal, and starting with a lower dose may be undertaken. Using a dose response model, 75 mg Q2W has been selected: all patients will be initially treated with 75 mg Q2W, and only those patients whose LDL-C levels remain equal to or higher than 70 mg/dL after 8 weeks of treatment will be dose up-titrated to 150 mg Q2W (at week 12). With this treatment scheme, most patients with primary hypercholesterolemia can be expected to achieve their target LDL-C level, with few patients reaching a level below 25 mg/dL.

Rationale for protocol design:

The objective of the present study is to demonstrate the superiority of alirocumab versus ezetimibe in Asia in patients at high cardiovascular risk and who require additional pharmacological management since their current maximally tolerated statin therapy failed to achieve the LDL-C treatment goal.

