9.3.3.1 Sampling time

Serum samples for total alirocumab concentration will be collected before IMP (pre-dose), after randomization at Week 0 (randomization visit). Additional samples will be collected before IMP (pre-dose) at Week 4, Week 12, Week 16 and Week 24, as per the study flowchart (see [Section 1.2](#)).

To collect information on the absorption phase, an optional PK sample will be collected at 5 days (± 2) after the Week 22 IMP injection or later.

Randomized patients who agree to have this additional PK sample will be required to provide additional consent prior to collection of the PK sample.

Exact date and time of last IMP administration and PK sampling are to be recorded.

9.3.3.2 *Sampling procedure*

Detailed procedure of sample preparation, storage and shipment will be described in the specific laboratory manual which will be provided to sites. Five (5) ml blood volume is to be collected for each PK sample.

9.3.3.3 *Bioanalytical method*

All PK samples will be analyzed by the Regeneron Clinical Bioanalysis Group.

PK samples will be analyzed for the determination of total alirocumab concentrations (ie, free alirocumab and alirocumab present in PCSK9: alirocumab complexes) using a validated enzyme-linked immunosorbent assay (ELISA).

PK samples can also be analyzed for the determination of the total and free PCSK9 levels using validated ELISA.

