### ***Observation period***

The period of safety observation starts from the time when the patient gives informed consent and is divided into the following periods:

- The PRE-TREATMENT period: defined as the time from the signed informed consent up to the first dose of double-blind IMP;
- The treatment-emergent adverse event (TEAE) period: defined as the time from the first dose of double-blind IMP up to the day of last dose of double-blind IMP injection+70 days (10 weeks) as residual effect of alirocumab is possible until 10 weeks after the discontinuation of double-blind IMP injection.

The TEAE period will include:

- The TREATMENT period defined as the time from the first dose of double-blind IMP up to the day of last dose of double-blind IMP injection + 21 days, as serum concentration of alirocumab is expected to be  $>10 \mu\text{g/mL}$  for approximately 21 days following administration of 150 mg, and because throughout the previous studies it was observed that when alirocumab concentrations declined below this concentration, decrease in effect on LDL-C is observed.
- The RESIDUAL TREATMENT defined as the time from the day of last dose of double-blind IMP injection + 22 days up to the day of last dose of double-blind IMP injection + 70 days (10 weeks).
- The POST-TREATMENT period: defined as the time starting the day after the end of the TEAE period (ie, 71 days after the day of last dose of double-blind IMP injection).

The on-study observation period is defined as the time from the day of first dose of double-blind IMP (capsule or injection, whichever comes first) until the last protocol planned visit of the patient. The last protocol planned visit is defined as the follow-up visit if done, or else 32 weeks after the randomization of the patient.

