## 2.1.7 Pharmacokinetics variables

Concentrations of total alirocumab, total and free proprotein convertase subtilisin/kexin type 9 (PCSK9) concentrations in serum are assessed at baseline (Week 0), Week 4, Week 12, Week 16, Week 24, and during the post-treatment follow-up visit (Week 32). To collect information on the absorption phase, an optional PK sample can be collected 5 days ( $\pm 2$ ) after the Week 22 IMP injection.

Pharmacokinetic variable is the total alirocumab concentration at each time point. Depending on the timing of the sample versus the previous injection,  $C_{\text{trough}}$ ,  $C_{\text{trough,av}}$ ,  $C_{\text{max}}$  and  $C_{\text{Follow-Up}}$  will be defined as follows:

- $C_{\text{max}}$ : alirocumab concentration sample taken 5 days  $\pm 2$  days after previous injection;
- $C_{\text{trough}}$ : alirocumab concentration sample taken 14 days  $\pm 6$  days after previous injection (may be just prior the next injection):
  - $C_{\text{trough,av}}$ : Alirocumab average trough concentrations (" $C_{\text{trough,av}}$ ") will be calculated for each patient as the mean of " $C_{\text{troughs}}$ " considered at steady state. The occurrence of

steady state will be assessed graphically, by plotting “Ctrough” throughout the study visits over all patients.

- CFollow-up: alirocumab concentration sample taken more than 21 days after last injection and no more than 14 weeks after last injection.

Alirocumab concentration and total and free PCSK9 concentration will be described following time windows as defined in [Section 2.5.4, Table 2](#).

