- For exploratory purpose, key safety analyses could also be provided according to up-titration status, ie, according to whether the patients remained on the 75 mg dose or whether they were up-titrated to 150 mg. These analyses will be exploratory and descriptive (no formal comparison per dose) as it is expected that there could be inherent differences in the baseline characteristics between those patients titrating to 150 mg and those remaining on 75 mg. In order to reduce the bias of this analysis, the period before the up-titration time point (planned at Week 12) will be analyzed separately since only the dose 75 mg is proposed for this time period and consequently the early events occurring before Week 12 can only be attributed to this dose. Therefore the descriptive analysis per dose will include any safety events occurring from the first injection post Week 12 IVRS/IWRS transaction to the end of the TEAE period. Baseline characteristics of patients receiving each dose will be summarized.

Analyses performed according to diabetes status will be done considering diabetic patients as patients with either type 1 or type 2 diabetes in the medical history e-CRF page (regardless of the ongoing status).

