#### **2.4.7 Analyses of anti-alirocumab antibodies variables**

The following summaries will be performed on the ADA population, taking into account all samples regardless of timing relative to the injections:

- ADA results (negative or positive) by time point and by treatment group and also according to up-titration status;
- Neutralizing status (negative or positive) by time point for positive ADA and by treatment group and also according to up-titration status;
- ADA titers using descriptive statistics (median, minimum and maximum) for positive ADA by time point and by treatment group and also according to up-titration status;
- Number (%) of patients with pre-existing ADA and number (%) of patients with treatment-emergent ADA positive response by treatment group, overall and according to up-titration status;
- Number (%) of patients with persistent/transient/indeterminate treatment-emergent ADA positive response by treatment group, overall and according to up-titration status;

- Time to onset of treatment-emergent ADA positive response using descriptive statistics by treatment group, overall and according to up-titration status.

Correlations between ADA parameters (eg, titers, treatment-emergent ADA positive status, neutralizing status) and safety and/or efficacy endpoints will be also explored (eg, scatter plot).

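### The by-dose concentration summaries in SAP 2.4.8 are confounded by the Week 8 LDL-C titration rule; a within-patient trough comparison should be added for the stated aim

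*SAP*

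**What the plan says.** SAP 2.4.8 summarises trough, maximum and follow-up alirocumab concentrations and free and total PCSK9 by treatment group and visit, and then adds: "These summaries will be also provided by dose in the alirocumab group to explore the impact of up-titration on concentrations". It plans no within-patient contrast and gives no caution about how patients come to be on each dose.

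The dose is set by response. Protocol section 4 says that "only those patients whose LDL-C levels remain equal to or higher than 70 mg/dL after 8 weeks of treatment will be dose up-titrated" at Week 12; Protocol 6.1 and 8.5 repeat the rule.

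On sampling, Protocol 9.3.3.1 states: "Additional samples will be collected before IMP (pre-dose) at Week 4, Week 12, Week 16 and Week 24". For the maximum concentration, SAP 2.1.7 says: "To collect information on the absorption phase, an optional PK sample can be collected 5 days" (plus or minus 2) after the Week 22 injection.

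Two neighbouring SAP sections treat the same issue differently. For safety analyses by up-titration status, the general rules in 2.4.5 warn of possible "inherent differences in the baseline characteristics between those patients titrating to 150 mg and those remaining on 75 mg" and analyse the period before Week 12 separately. For antibodies, 2.4.7 tabulates "ADA results (negative or positive) by time point and by treatment group and also according to up-titration status".

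**The concern.** Up to Week 12 every alirocumab patient is on 75 mg. From then on, the 150 mg rows hold only patients whose Week 8 LDL-C was at or above the cut-off, and the 75 mg rows hold the rest. Anything that affects both Week 8 LDL-C and concentration therefore enters the 150 mg versus 75 mg comparison together with the dose. Comparing 150 mg at Week 24 with all patients at Week 12 does not solve this, because the Week 12 row pools future up-titrated and non-up-titrated patients.

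Evaluating the PK of alirocumab is a secondary objective (Protocol 5.2, SAP 1.2.2). A reader of the planned table will naturally take the ratio of its rows as the concentration gain from up-titration, although it is not a clean estimate of that gain. The same patients give trough samples before and after the decision, so a cleaner comparison is available but not planned.

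**Working it through.** SAP 2.4.8 states no figure, so there is none to reproduce. The check has four steps.

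**1. What the rule selects.** Week 8 LDL-C = baseline × (1 − reduction). At the reduction of about 50% that Protocol section 4 expects with 75 mg, a baseline of 140 mg/dL gives 140 × 0.50 = 70, so that patient is up-titrated with an average response. A patient starting at 100 mg/dL is up-titrated only if the reduction is 30% or less (100 × 0.70 = 70). The rule therefore selects on baseline LDL-C and on response.

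**2. What each comparison estimates.** Write log trough = patient level + ln(dose ratio) if on 150 mg + noise.
- By dose at Weeks 16 and 24: ln(dose ratio) + (mean patient level of up-titrated minus that of the others).
- Within patient, after minus before: ln(dose ratio). The patient level cancels.

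**3. Size, under stated assumptions.** Simulation of 1,000,000 patients per setting.
- From the documents: mean reduction 50% (Protocol section 4); SD 25 percentage points (Protocol 11.1, there assumed for the primary endpoint); cut-off 70 mg/dL.
- Assumed: baseline LDL-C mean 110 and SD 35 mg/dL, with values below 70 dropped; residual log-SD 0.25; true 150/75 mg trough ratio 2.0; between-patient log-SD ω of 0.3 to 0.7; correlation r between exposure and percent LDL-C reduction of 0 to 0.6.

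About 31% are up-titrated. Up-titrated and other patients differ in mean baseline (136 versus 106 mg/dL) and mean reduction (26.2% versus 60.6%). The gap in reduction is (60.6 − 26.2)/25 = 1.376 SD. When exposure is unrelated to baseline LDL-C, the by-dose ratio is therefore close to 2.0 × exp(−1.376 × ω × r). For ω = 0.5 and r = 0.4: 2.0 × exp(−0.275) = 1.52, which agrees with the simulation.

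| r | ω = 0.3 | ω = 0.5 | ω = 0.7 |
|---|---|---|---|
| 0 | 2.00 | 2.00 | 2.00 |
| 0.2 | 1.84 | 1.75 | 1.65 |
| 0.4 | 1.70 | 1.52 | 1.36 |
| 0.6 | 1.56 | 1.32 | 1.12 |

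The direction is not fixed. With ω = 0.5, r = 0 and a correlation of +0.2 between exposure and baseline LDL-C, the by-dose ratio is 2.16. At ω = 0.5 the scenarios therefore run from 1.32 to 2.16.

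The within-patient ratio in up-titrated patients is 2.00 in every setting without a time trend. With a 10% upward trend it reads 2.0 × 1.1 = 2.20 on its own; divided by the same ratio in patients staying on 75 mg, it returns 2.20/1.10 = 2.00. That reference group is needed.

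**4. Which samples can be paired.** The Week 12 pre-dose sample follows six 75 mg injections (Weeks 0 to 10, Protocol 6.1). The Week 24 sample follows six injections at the assigned dose (Weeks 12 to 22), and the Week 16 sample only two (Weeks 12 and 14). The Week 12 analysis window in SAP 2.5.4 closes at the first injection from the kit allocated at up-titration, so it is a pre-titration value. PCSK9 is measured in the same samples. Maximum concentration is scheduled only after the Week 22 injection, and follow-up concentration only after the last injection, so neither has a scheduled pre-titration partner.

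**The case against.** The strongest reply is that this is a descriptive summary with an exploratory purpose. No test is attached, no dose ratio is formally estimated, and no PK variable is in the testing hierarchy. SAP 2.4.8 also allows further plots and, if considered necessary, a population PK model. All of this is right, and it limits the weight of the point. It does not remove it: the extra plots and the model are optional, the model would be reported outside the study report, and the by-dose summary is the only firm output aimed at up-titration.

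A reader might infer that the planned table will understate the dose effect. The documents do not support that as a certainty. SAP 2.1.4 says that "when alirocumab concentrations declined below this concentration, decrease in effect on LDL-C is observed", but this explains the 21-day treatment period by the decline after dosing. It does not say that patients at or above 70 mg/dL at Week 8 have low troughs, and no between-patient correlation is given. Nor is the 150 mg group simply the poor responders, because the cut-off is absolute.

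A reader might also infer that the table could hide a doubling altogether. Even the most extreme case above still shows a gain (1.12), and it needs the widest spread and the strongest correlation examined.

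Finally, for patients dosed as allocated, grouping by up-titration status is the same as grouping by dose at Weeks 16 and 24. That is correct. Regrouping alone changes only the Week 4 and Week 12 rows, so the within-patient ratio is the essential addition. Actual dose also remains informative, since SAP 2.2.1 foresees kits from before Week 12 being used after the up-titration visit.

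**Conclusion.** The point holds as one of confounding. At Weeks 16 and 24 the comparison of 150 mg with 75 mg mixes dose with the LDL-C response and baseline LDL-C that determined the dose. The SAP acknowledges non-comparable dose groups for safety but not for PK. Understatement is the likelier direction if lower exposure leads to higher Week 8 LDL-C, but the documents establish neither size nor direction. The range of about 1.3 to 2.2 around a true 2.0 rests on the assumed doubling, ω = 0.5 and the assumed correlations; with no link between concentration and Week 8 LDL-C the error is zero.

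The consequence is confined to how a descriptive PK table is read. The better method applies to trough concentration and PCSK9 only; for maximum and follow-up concentration, a caution is all that the scheduled samples allow. The change is worth making because it serves the SAP's own stated aim at very little cost.

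**What to change.** In SAP 2.4.8, keep the by-dose summaries and add, for trough concentration and free and total PCSK9:

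- Summaries by up-titration status (as defined under Titration in SAP 2.4.3.1) at Weeks 4, 12, 16 and 24, following the pattern of 2.4.7. The Week 4 and Week 12 rows show directly whether patients later up-titrated already differed on the same dose.
- The geometric mean within-patient ratio of Week 24 to Week 12 in up-titrated patients, with the same ratio in patients staying on 75 mg as the time reference. Give Week 16 to Week 12 as well, noting that steady state may not yet be reached; SAP 2.1.7 leaves steady state to graphical assessment.

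Extend the caution in SAP 2.4.5 on non-comparable dose groups to all PK summaries by dose, including maximum and follow-up concentration, and state that these two have no pre-titration sample.

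The cost is a few lines of SAP text and one extra descriptive table. No new samples or visits are needed.

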### **2.5 DATA HANDLING CONVENTIONS**

#### **2.5.1 General conventions**

The following formulas will be used for computation of parameters.

##### ***Time from diagnosis***

Time from diagnosis (years) = (Date of informed consent – Date of diagnosis\*) / 365.25.

(\*): In case the month of diagnosis would be missing, it will be put equal to JANUARY if the year of diagnosis equals the year of informed consent; it will be put equal to JUNE otherwise.

##### ***Medical History***

“Peripheral Arterial Disease” history is defined as follows, using combinations of the corresponding pre-listed medical history items of the e-CRF page “Cardiovascular history and cardiovascular risk factors”:

- Intermittent claudication (linked to PAD) TOGETHER WITH ankle-brachial index  $\leq 0.90$   
*Or*

- Intermittent claudication (linked to PAD) TOGETHER WITH peripheral revascularization procedure (angioplasty, stenting) for PAD or peripheral revascularization surgery (arterial bypass) for PAD  
*Or*
- Critical limb ischemia TOGETHER WITH peripheral revascularization procedure (angioplasty, stenting) for PAD or thrombolysis for PAD or peripheral revascularization surgery (arterial bypass) for PAD.

### ***Date of last dose of IMP***

The date of last injection is equal to the last date of administration reported on injection administration case report form page, or missing if the last administration date is unknown.

### ***Lipid variable, laboratory safety variables***

For data below the lower limit of quantification (LLOQ)/limit of linearity, half of the lower limit value (ie, LLOQ/2) will be used for quantitative analyses. For data above the upper limit of quantification (ULOQ)/limit of linearity, the upper limit value (ie, ULOQ) will be used for quantitative analyses.

### ***2.5.2 Data handling conventions for secondary efficacy variables***

See [Section 2.4.4.2](#) Analysis of secondary endpoints.

### ***2.5.3 Missing data***

For categorical variables, patients with missing data are not included in calculations of percentages unless otherwise specified. When relevant, the number of patients with missing data is presented.

### ***Handling of baseline definition if time of first double-blind administration or time of assessment at Week 0 visit is missing***

If the time of the first double-blind administration or time assessment at Week 0 visit is missing then the baseline value is defined as the last available value obtained before or on the day of the first double-blind IMP administration.

### ***Handling of computation of treatment duration and compliance if investigational medicinal product end of treatment date is missing***

If the last or first injection date (capsule administration respectively) is missing, the injection (capsule respectively) exposure duration and compliance will be left as missing.

### ***Handling of safety and efficacy analysis periods and survival analysis if investigational medicinal product end of treatment date is missing***

If the last injection date is missing, then this date is imputed to the earliest between

- The last day of the month and year, when applicable or else the 31st of December of the year;
- The date of the end of treatment visit (Week 24 visit for completer, early end of treatment visit for patients who prematurely discontinued the IMP);
- And the date of the last contact;

in order to determine the end of the safety and efficacy analysis periods.

If the last capsule intake date is missing, the last known capsule intake date is used to define the end of the efficacy treatment period.

#### ***Handling of medication missing/partial dates***

No imputation of medication start/end dates or times will be performed. If a medication date or time is missing or partially missing and it cannot be determined whether it was taken prior or concomitantly, it will be considered a prior, concomitant, and post-treatment medication.

#### ***Handling of adverse events with missing or partial date/time of onset, worsening, seriousness***

Missing or partial AE onset dates and times will be imputed so that if the partial AE onset date/time information does not indicate that the AE started prior to treatment or after the TEAE period, the AE will be classified as treatment-emergent. No imputation of AE end dates/times will be performed. These data imputations are for categorization purpose only and will not be used in listings. No imputation is planned for date/time of AE resolution.

